The concentration of the relevant concomitant medications will be measured using samples collected predose and 2 hours postdose of branebrutinib or placebo on both Day 1 and Day 29 (Week 4; at which point accumulation of branebrutinib and its metabolites is expected to achieve steady-state). Bioanalytical analysis of all relevant concomitant medications will be conducted post-hoc. The doses of the concomitant drugs and the time they are taken, will be carefully recorded at all times (including Day 1 in Week 0 and on Day 29 in Week 4). The doses of concomitant medications will be carefully recorded at all times. Actual and dose-normalized trough concentrations will be listed, summarized, and compared between posttreatment and pretreatment of branebrutinib and PBO separately; other covariates such as MTX use, gender, etc. can be added to the comparison as needed.

Detailed instructions for PK sample collection for the relevant concomitant medications, labeling, processing, storage, shipping, and disposition are provided in the Laboratory Manual. Plasma samples will be analyzed for all relevant concomitant medications by available validated assays. The results of post hoc analyses will not be recorded in the CSR.

[figure not shown]

Protocol Amendment No.: 04

RA 8.7 Health Economics OR Medical Resource Utilization and Health Economics

Health Economics/Medical Resource Utilization and Health Economics parameters will not be evaluated in this study.

RA 9 STATISTICAL CONSIDERATIONS

RA 9.1 Sample Size Determination

Sample size is calculated based on the estimated effect size for the primary endpoint comparison between branebrutinib and PBO treatment groups. The primary endpoint for the RA sub-protocol is the ACR50 response at Week 12.

Estimates for PBO response rates, treatment differences, and common standard deviations were obtained from the published literature. ^{92,93} Sample size justification is provided below for the RA sub-protocol:

Assuming a total sample size of 80 subjects randomized in a blinded fashion at a 3:1 ratio to branebrutinib (60 subjects) or PBO (20 subjects), there will be 82% power to detect a treatment difference of 30% assuming the PBO response rate is 15% in ACR50 at Week 12, given a 1 sided, two-group test of a difference in binomial proportions with a 5% level of significance.

RA 9.2 Populations for Analyses

For purposes of analysis, the following populations are defined:

Population	Description

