Enrolled Set	All subjects who sign informed consent.
FAS	All subjects who are randomized. Following the intent-to-treat principle, subjects will be analyzed according to the treatment assigned at randomization. The FAS will be the primary efficacy analysis population. This is the same as the intent-to-treat population.
Full Abatacept Analysis Set (FAAS)	All FAS subjects who are dispensed Abatacept treatment.
PPS	A subset of the FAS wo are compliant with study treatment and who do not have any statistically relevant protocol deviations that may impact the primary efficacy endpoint assessments. The PPS will be analyzed according to the treatment assigned at randomization. The PPS will be a supportive efficacy analysis population.
Safety Analysis Set	All randomized subjects who receive at least 1 dose of double-blind study treatment. Subjects will be analyzed according to treatment received. In cases where the subjects take the incorrect treatment, the following scenario will be considered. • For subjects who should be receiving branebrutinib treatment during the blinded treatment period, if the subject took any placebo dose, the subject will still be counted in the branebrutinib treatment group for safety analysis set unless the subject took placebo throughout the entire course. • For subjects who should be receiving placebo treatment during double the blinded treatment period, if the subject took any

Population Description			
	branebrutinib dose, the subject will be counted in the branebrutinib		
treatment group for safety analysis set.			
PK population for	All randomized subjects who receive at least 1 dose of branebrutinib		
branebrutinib	and have any available branebrutinib concentration data.		
	All randomized subjects who receive at least 1 dose of double-blind		
Biomarker	study treatment and have at least 1 posttreatment biomarker		
	measurement. Subjects will be analyzed according to treatment		
	received.		

RA 9.3 Endpoints

The following sections outline the efficacy endpoints for the RA sub-protocol:

RA 9.3.1 Primary Endpoint

• ACR50 response at Week 12 compared to baseline

RA 9.3.2 Secondary Endpoints

The following are the secondary efficacy endpoints as defined at Week 12:

- Change from baseline in:
 - o DAS28-CRP
 - o DAS28-ESR
 - o SDAI
 - o CDAI
- ACR20 response compared to baseline
- ACR70 response compared to baseline

RA 9.3.3 Additional Endpoints

The following are the additional efficacy endpoints as defined at Week 12:

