Efficacy data will be summarized using the FAS. Data will be summarized using descriptive statistics (n, mean, standard deviation, median, minimum, and maximum), unless otherwise specified, for continuous variables and frequency distributions (counts and percentages) for categorical variables. Efficacy data will be summarized separately for each sub-protocol and with each sub-protocol combined for variables that are similar among the sub-protocols.

Protocol Amendment No.: 04

Approved v2.0 930168072 2.0

For the RA sub-protocol, data through Week 12 will be presented for:

- Branebrutinib
- Branebrutinib PBO

After Week 12, data may be presented for the following treatments for the RA sub-protocol:

- Branebrutinib followed by Abatacept
- PBO followed by Abatacept
- Branebrutinib and PBO followed by Abatacept

Endpoint	Statistical Analysis Methods
	General Analysis Methodology Response rates of branebrutinib compared to PBO for the primary endpoint will be analyzed using a Chi-square test. The 95% CI for each treatment group response rate and the difference in response rate for branebrutinib compared to PBO will be provided. If expected cell counts are not sufficient, then Fisher's exact test will be used. P-values will be provided.
Primary	Supportive Analyses A Bayesian approach combines current study PBO data and PBO data from historical RA studies will be employed. The probability of response rate difference between branebrutinib and PBO greater than 30% will be calculated with derived posterior distribution. Fixed borrowing or dynamic borrowing method will be implemented. Imputation Method Nonresponder imputation will be used for binary endpoints for subjects who discontinue study treatment early, start a protocol-prohibited medication/therapy prior to the specified timepoint, or otherwise have missing endpoint data for the specified timepoint. Other imputation methods may be considered for sensitivity analyses and will be described in the SAP if used.

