Secondary/ Additional	General Analysis Methodology Response rates of branebrutinib compared to PBO for binary endpoints (responder/nonresponder) will be analyzed using a Chi-square test. The 95% CI for each treatment group response rate and the difference in response rate for branebrutinib compared to PBO will be provided. If expected cell counts are not sufficient, then Fisher's exact test will be used. The same criteria used for primary endpoints for the nonresponder imputation will be applied for all secondary/additional binary endpoints. Continuous endpoints (change from baseline values) will be analyzed using analysis of covariance. The baseline value of the endpoint being tested will be added into the model as a covariate. Treatment differences based on

Protocol Amendment No.: 04

Endpoint	Statistical Analysis Methods
	least-squares means and corresponding 2-sided 95% CIs will be provided for the
	difference between branebrutinib and PBO.
	Supportive analyses for continuous endpoints may be performed using MMRM
	to investigate response over time. Missing data are addressed in these models
	and assumed to be MAR.
	Testing Strategy for Secondary Endpoints
	There will be no alpha level adjustment for multiple endpoint testing.

RA 9.4.1.1 Subgroup Analyses

Subgroup analyses will be conducted for the primary and secondary efficacy endpoints on the FAS population. Subgroups that may be evaluated include the following:

- Gender
- Race
- Tobacco use

Additional subgroups defined for descriptive summaries may be specified in the SAP.

RA 9.4.2 Safety Analyses

Safety data will be descriptive in nature and will be summarized using the Safety Analysis Set. Data will be summarized using descriptive statistics (n, mean, standard deviation, median, minimum, and maximum), unless otherwise specified, for continuous variables and frequency distributions (counts and percentages) for categorical variables. Safety data will be summarized separately for each sub-protocol and with all sub-protocols combined.

For the RA sub-protocol, data through Week 12 will be presented for:

- Branebrutinib
- Branebrutinib PBO

After Week 12, data may be presented for the following treatments for the RA sub-protocol:

- Branebrutinib followed by Abatacept
- PBO followed by Abatacept
- Branebrutinib and PBO followed by Abatacept

RA 9.4.2.1 Adverse Events

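### RA secondary endpoints: Fisher's test as the small-count fallback is needlessly conservative for ACR70; at assumed rates Boschloo's test gains about 6–19 points of power two-sided, or 2–9 at one-sided 5%

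*Combined protocol and SAP*

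**What the plan says.** Section RA 9.3.2 lists "ACR70 response compared to baseline" among the secondary endpoints at Week 12. The rule that governs it is in the Secondary/Additional row of the methods table in RA 9.4.1: "Response rates of branebrutinib compared to PBO for binary endpoints (responder/nonresponder) will be analyzed using a Chi-square test". The same row switches to Fisher's exact test under one condition, worded only as "If expected cell counts are not sufficient". The Primary row applies the same pair of tests to ACR50.

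Neither row says what count is sufficient or whether the p-value is one- or two-sided. RA 9.1 sizes the sub-protocol "at a 3:1 ratio to branebrutinib (60 subjects) or PBO (20 subjects") and makes a power claim for ACR50 alone: "there will be 82% power to detect a treatment difference of 30% assuming the PBO response rate is 15% in ACR50 at Week 12". That claim is for a one-sided comparison at the 5% level. No ACR70 response rate and no ACR70 power are given. The secondary endpoints carry no multiplicity adjustment. Nonresponder imputation applies to secondary binary endpoints too, so the denominators stay at 60 and 20.

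**The concern.** With only 20 placebo subjects, a low-response endpoint will often have a small expected count in the placebo responder cell. The fallback may then be the usual analysis for ACR70 rather than a rare exception. Fisher's test conditions on the total number of responders, and at 60 versus 20 with low rates its attainable levels lie well below 5%. ACR70 p-values would then be larger than control of the 5% level requires. A real ACR70 difference would more often look unconvincing in the Week 12 analysis, which RA 9.4.4 says will inform early planning decisions.

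**Working it through.** **Plan's own figure.** Pooled rate = (60×0.45 + 20×0.15)/80 = 30/80 = 0.375. Null SE = √[0.375×0.625×(1/60 + 1/20)] = 0.125. Alternative SE = √[0.45×0.55/60 + 0.15×0.85/20] = √0.0105 = 0.1025. Power = Φ[(0.30 − 1.645×0.125)/0.1025] = Φ(0.921) ≈ 82%. The stated 82% is reproduced as a one-sided 5% chi-square calculation.

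**Trigger.** With R responders in total, the expected placebo responder count is 20×R/80 = R/4. It is below 5 when R < 20. (R > 60 also triggers, through the nonresponder cell, but that is irrelevant at low rates.) The expected R is 60×p_B + 20×p_P. At the ACR50 design rates this is 27 + 3 = 30, and the fallback is used in only 0.5% of trials.

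**Size and power.** All 61×21 = 1,281 possible tables were enumerated. The planned rule is Fisher if any expected count is below 5, otherwise chi-square. The Boschloo p-value is the maximum, over the common response rate, of the null probability of all tables whose Fisher p-value is no larger than the one observed. Two-sided Boschloo is ordered by the two-sided Fisher p-value. ACR70 rates are assumptions. Differences come from unrounded figures.

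| Branebrutinib vs placebo | Expected R | Fallback used | Two-sided 5%: plan → Boschloo | One-sided 5%: plan → Boschloo |
|---|---|---|---|---|
| 20% vs 2% | 12.4 | 98% | 39.0 → 58.2 (+19.2) | 58.4 → 66.9 (+8.5) |
| 20% vs 5% | 13 | 97% | 22.9 → 36.2 (+13.3) | 36.8 → 43.7 (+6.8) |
| 25% vs 5% | 16 | 84% | 44.4 → 56.8 (+12.4) | 59.5 → 64.8 (+5.2) |
| 30% vs 5% | 19 | 56% | 66.2 → 74.1 (+7.9) | 79.1 → 81.5 (+2.5) |
| 20% vs 10% | 14 | 94% | 9.2 → 15.5 (+6.4) | 16.5 → 20.2 (+3.7) |
| 25% vs 10% | 17 | 76% | 21.8 → 29.4 (+7.6) | 33.9 → 37.3 (+3.4) |
| 30% vs 10% | 20 | 46% | 40.3 → 46.2 (+5.9) | 55.2 → 57.0 (+1.7) |

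At 35% vs 10% the expected R is 23. The fallback is used in 19% of trials and the two-sided gain is about 3.5 points.

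**The ordering matters.** If Boschloo is run one-sided at 2.5% and compared with the two-sided plan, the gains at 20% vs 2%, 20% vs 5%, 25% vs 5% and 30% vs 5% are 9.8, 6.5, 6.4 and 4.3 points. Over the whole assumed range they are about 3–10.

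**Level.** Fisher's maximum size is 3.6% two-sided and 3.1% one-sided. Boschloo's is 4.9% either way. At a common rate of 10% the two-sided size is 2.4% for the planned rule and 4.1% for Boschloo; at 15% it is 2.9% and 4.7%.

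**A comparison that needs no assumed rates.** In all 1,281 tables, one- and two-sided, Boschloo's p-value is no larger than Fisher's. For 11/60 vs 0/20 (smallest expected count 11/4 = 2.75) the two-sided p-values are 0.039 by chi-square, 0.057 by Fisher and 0.042 by Boschloo. For 16/60 vs 1/20 (17/4 = 4.25) they are 0.040, 0.057 and 0.042. In both tables the unstated threshold decides which side of 0.05 the planned result falls.

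**Fallback only.** The table applies Boschloo to every outcome. If it replaces Fisher only below 20 responders, the same enumeration gives gains less than one point smaller in every row.

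**The case against.** Chi-square with Fisher for small counts is conventional and specified in advance, and Fisher controls type I error. ACR70 is a secondary endpoint with no power claim, no alpha control and no decision rule attached. Estimates and 95% intervals will be reported whichever test is used. RA 9.4 describes its text as a summary and leaves detail to an SAP that is still to be finalized. All of this stands, and it keeps the point minor. It does not remove the advantage of a test that controls the same level and never gives a larger p-value than Fisher's.

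Three stronger readings are tempting and are not supported.

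- From the placebo 2–5% rows, a reader might infer that the plan costs ACR70 a fixed 8–19 points. The documents give no ACR70 rate, no sidedness for the p-value and no threshold. That range needs two-sided testing, low placebo rates and one particular ordering. At placebo 10% the two-sided gain is about 6–8 points, and at the one-sided 5% used for sizing it is about 2–9 over the assumed range.
- A reader might infer that these endpoints are always tested at about half the nominal level. That is fair at common rates of 10–15%, but the planned rule's two-sided size reaches 5.1% at other common rates.
- A reader might infer that the primary analysis is affected. At 45% versus 15% Boschloo gains nothing: 71.4% against 71.9% for the plan two-sided, and 82.5% for both one-sided.

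**Conclusion.** The concern holds as a minor improvement to the secondary/additional row, not as an error in the primary analysis. If the trigger is any expected count below 5, Fisher will be the test in 46–98% of trials at assumed ACR70 rates of 20–30% versus 2–10%, and less often if branebrutinib does better. Over that range Boschloo gains about 6–19 points two-sided when ordered by the two-sided Fisher p-value, about 3–10 as a one-sided test at 2.5%, and about 2–9 at one-sided 5%. The sizes of these gains rest on the assumed rates, trigger and sidedness. That Boschloo's p-value never exceeds Fisher's, and that its maximum size is 4.9%, depends only on the 60 versus 20 split.

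**What to change.** In the Secondary/Additional row of RA 9.4.1, and in the SAP, replace Fisher's test with Boschloo's exact unconditional test as the small-count fallback. State three things with it: whether the p-value is one- or two-sided, the ordering statistic (for example the two-sided Fisher p-value), and the trigger (any expected count below 5). Fix these before the Week 12 lock in RA 9.4.4, because that is when unblinded results are first reviewed.

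Leave the primary ACR50 chi-square test unchanged. Keeping chi-square for secondary results with 20 or more responders also leaves the planned rule's 5.1% two-sided maximum in place, since that comes from the chi-square part; the 4.9% bound belongs to Boschloo applied to every table.

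The cost is a few sentences of wording and standard software. No new data or subjects are needed.

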	Change from baseline in RAMRIS scores of synovitis, osteitis (bone marrow edema), bone erosion, and cartilage loss (joint-space narrowing)					
	Change from baseline in the EQ-5 D-5 L score					
	Change from baseline in PROMIS Fatigue 6 a					
Additional	 					
Open-label abatacept therapy: Week 12 to	Week 24					
open-label abatacept therapy. Week 12 to	Additional:					
	 Changes from Week 12 at Week 24 in efficacy measures, including DAS28-CRP and DAS28-ESR, SDAI, and CDAI 					
• To evaluate the efficacy at Week 24	ACR20, ACR50, and ACR70 response at Week 24 based on activity at Week 12 after pretreatment with branebrutinib or PBO (treatment effect of abatacept following treatment with branebrutinib versus PBO)					
of switching from branebrutinib or PBO to abatacept at Week 12 in the	Change from Week 12 to Week 24 in autoantibody titers, change from Week 12 to Week 24 in BTK occupancy					
treatment of subjects with moderate to severe RA on a stable background of MTX who have had an inadequate	• Change from Week 12 to Week 24 in ACR component assessments:					
response to MTX	 Tender/Painful Joint Count (68) 					
1	- Swollen Joint Count (66)					
	 PGA of Arthritis 					
	 Subject Global Assessment of Disease Activity 					
	- hsCRP					
	– HAQ-DI					

Clinical Protocol IM014029 - RA
BMS-986195 Branebrutinib

RA Sub-protocol Objectives and Endpoints:

Ob	ojectives	Endpoints
		 Change from Week 12 to Week 24 in RAMRIS scores of synovitis, osteitis (bone marrow edema), bone erosion, and cartilage loss (joint-space narrowing) Change from Week 12 to Week 24 in the EQ-5 D-5 L score
		Change from Week 12 to Week 24 in PROMIS Fatigue 6 a
	lditional anebrutinib followed by open-label abata	acept therapy: Day 1 to Week 24
•	To evaluate the efficacy at Week 24 of branebrutinib or PBO treatment followed by abatacept treatment in subjects with moderate to severe RA	 Changes from baseline at Week 24 in efficacy measures including DAS28-CRP, DAS28-ESR, SDAI, and CDAI ACR20, ACR50, and ACR70 response at Week 24 compared to
	on a stable background of MTX who have had an inadequate response to MTX	 Change from baseline at Week 24 in PROMIS Fatigue 6 a
Sa	fety	
•	To evaluate the safety and tolerability at Week 24 of switching at Week 12 from branebrutinib or PBO to abatacept in subjects with RA	Number and proportion of subjects experiencing SAEs, AEs, and abnormalities in laboratory parameters, vital signs, and ECGs
Ex	ploratory	

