To compare the efficacy of branebrutinib with PBO at Week 12 in the treatment of subjects with moderate to severe RA on a stable background of MTX who have had an inadequate response to MTX	 Secondary: Changes in efficacy measures, including DAS28-CRP and DAS28-ESR, SDAI, and CDAI ACR20 and ACR70 response compared to baseline Additional: Change from baseline in autoantibody titers, change from baseline in BTK occupancy Change from baseline in ACR component assessments: Tender/Painful Joint Count (68) Swollen Joint Count (66) PGA of Arthritis Subject Global Assessment of Disease activity hsCRP HAQ-DI Change from baseline in RAMRIS scores of synovitis, osteitis (bone marrow edema), bone erosion, and cartilage loss (joint-space narrowing) Change from baseline in the EQ-5 D-5 L score Change from baseline in PROMIS Fatigue 6 a
Additional	
Open-label abatacept therapy: Week 12 to Week 24	
To evaluate the efficacy at Week 24 of switching from branebrutinib or PBO to abatacept at Week 12 in the treatment of subjects with moderate to severe RA on a stable background of MTX who have had an inadequate response to MTX	 Additional: Changes from Week 12 at Week 24 in efficacy measures, including DAS28-CRP, DAS28-ESR, SDAI, and CDAI ACR20, ACR50, and ACR70 response at Week 24 based on activity at Week 12 after pretreatment with branebrutinib or PBO

RA Table 4 Objectives and Endpoints

Objectives	Endpoints
	(treatment effect of abatacept following treatment with branebrutinib versus PBO)
	Change from Week 12 to Week 24 in autoantibody titers, change from Week 12 to Week 24 in BTK occupancy
	Change from Week 12 to Week 24 in ACR component assessments:
	 Tender/Painful Joint Count (68)
	- Swollen Joint Count (66)
	 PGA of Arthritis
	 Subject Global Assessment of Disease Activity
	– hsCRP
	– HAQ-DI
	Change from Week 12 to Week 24 in RAMRIS scores of synovitis, osteitis (bone marrow edema), bone erosion, and cartilage loss (joint-space narrowing)
	Change from Week 12 to Week 24 in the EQ-5 D-5 L score
	Change from Week 12 to Week 24 in PROMIS Fatigue 6 a

Additional

Branebrutinib followed by open-label abatacept therapy: Day 1 to Week 24

To evaluate the efficacy at Week 24 of branebrutinib or PBO treatment followed by abatacept treatment in subjects with moderate to severe RA on a stable background of MTX who have had an inadequate response to MTX

Additional:

- Changes from baseline at Week 24 in efficacy measures, including DAS28 CRP, DAS28-ESR, SDAI, and CDAI

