- ACR20, ACR50, and ACR70 response at Week 24 compared to baseline
- Change from baseline at Week 24 in PROMIS Fatigue 6 a

Safety

To evaluate the safety and tolerability of switching from branebrutinib or PBO to abatacept in subjects with RA

Number and proportion of subjects experiencing SAEs, AEs, and abnormalities in laboratory parameters, vital signs, and ECGs

Exploratory

[figure not shown]
• Evaluate the PK of branebrutinib and metabolites of clinical interest

Protocol Amendment No.: 04 Date: 01-Dec-2021

225

; RNA = ribonucleic acid;

Simplified Disease Activity Index;

RA 4 STUDY DESIGN

;

RA = rheumatoid arthritis;

RA 4.1 Overall Design

This is a double-blind, PBO-controlled multicenter study to assess the effect of branebrutinib treatment and branebrutinib followed by abatacept (also named BMS-188667 and OrenciaTM) 125 mg SC QW in subjects with moderate to severe adult-onset RA.

SAE = serious adverse event;

SDAI =

- The RA study population will consist of male and female subjects aged 18 years (or age of majority) to 75 years inclusive at screening with moderate to severe adult-onset RA.
- Approximately 80 subjects will be randomized to the RA sub-protocol. Sample size considerations are presented in Section RA 9.1 Sample Size Determination.
- For all subjects there will be a 12-week double-blind PBO-controlled treatment period in which subjects will receive branebrutinib 9 mg or branebrutinib PBO. Note: the last day of dosing of branebrutinib or PBO in the RA sub-protocol should be the day prior to the Week 12/Day 85 visit.
- Blinded treatment assignment will be conducted by randomization on Day 1 and managed by IRT. Subjects will undergo screening evaluations to determine eligibility within 28 days prior to administration of study medication. After successfully meeting entry criteria and completing

screening assessments, subjects will be randomized (3:1 ratio) in a blinded manner to branebrutinib 9 mg or PBO QD.

- No stratification will be imposed at randomization in this sub-protocol.
- The total duration of participation in the RA sub-protocol will be approximately 32 weeks and will be divided into the following periods: screening (up to 4 weeks), double-blind PBO-controlled treatment with branebrutinib for 12 weeks (Week 0 to Week 12), open-label abatacept treatment for an additional 12 weeks (Week 12 to Week 24), and follow-up (4 weeks).

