- An investigator who receives an investigator safety report describing SAEs or other specific safety information (eg, summary or listing of SAEs) from the Sponsor will file it along with the IB and will notify the IRB/IEC, if appropriate according to local requirements.

The Sponsor or designee will be reporting AEs to regulatory authorities and ethics committees according to local applicable laws including European Directive 2001/20/EC and FDA Code of Federal Regulations (CFR) 21 CFR Parts 312 and 320. A SUSAR is a subset of SAEs and will be reported to the appropriate regulatory authorities and investigators following local and global guidelines and requirements.

RA 8.2.6 Pregnancy

If, following initiation of the study treatment, it is subsequently discovered that a subject is pregnant or may have been pregnant at the time of study exposure, including during at least 5 half-lives after product administration, the investigator must immediately notify Drug Safety of this event and complete and forward a Pregnancy Surveillance Form to Drug Safety within 24 hours of awareness of the event and in accordance with SAE reporting procedures described in APPENDIX 3.

Protocol-required procedures for study discontinuation and follow-up must be performed on the subject.

Follow-up information regarding the course of the pregnancy, including perinatal and neonatal outcome and, where applicable, offspring information must be reported on the Pregnancy Surveillance Form.

Clinical Protocol
BMS-986195
IM014029 - RA
Branebrutinib

Any pregnancy that occurs in a female partner of a male study subject should be reported to Drug Safety. In order for the Sponsor or designee to collect any pregnancy surveillance information from the female partner, the female partner must sign an ICF for disclosure of this information. Information on this pregnancy will be collected on the Pregnancy Surveillance Form.

RA 8.2.7 Laboratory Test Result Abnormalities

The following laboratory test result abnormalities should be captured on the AE eCRF page.

- Any laboratory test result that is clinically significant or meets the definition of an AE or SAE
- Any laboratory test result abnormality that required the subject to have study treatment discontinued or interrupted
- Any laboratory test result abnormality that required the subject to receive specific corrective therapy

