TEAEs are defined as AEs that occur after the subject received first dose of study treatment or if a preexisting condition worsens in severity or becomes serious after receiving the first dose of study treatment up to 30 days after the last dose of study treatment. All reported TEAEs, SAEs, deaths, AEs leading to study treatment discontinuation, and target AEIs will be summarized by MedDRA system organ class and preferred term.

Protocol Amendment No.: 04

RA 9.4.2.2 Clinical Laboratory Tests

Laboratory parameters will be summarized as absolute and change from baseline values by visit. Baseline values are defined as the last nonmissing value prior to the first dose of study treatment. Marked abnormalities summarized by visit and shift tables will also be provided. For clinical laboratory test results, marked abnormalities will be defined in the SAP.

RA 9.4.2.3 Vital Signs and ECGs

Vital signs and ECGs will be summarized as absolute and change from baseline values by visit. Baseline values are defined as the last nonmissing value prior to the first dose of study treatment. Marked abnormalities will be summarized by visit as well. For vital signs and ECGs, marked abnormalities will be defined in the SAP.

RA 9.4.3 Other Analyses

The PK, PD, and exploratory biomarker analyses will be described in the SAP finalized before database lock. Any population PK analysis and PD analyses will be presented separately from the main CSR.

RA 9.4.4 Analysis and Reporting

After all subjects in the RA sub-protocol have completed Week 12 efficacy assessments or discontinued treatment/study prior to Week 12, a database lock, inclusive of efficacy, safety, PK and PD, will occur for the RA sub-protocol. Analysis using data up to 12 weeks will be performed. Results of this 12-week analysis (100% of participants in RA sub-protocol) will be reviewed by an unblinded team that is independent of the study team responsible for study conduct. This activity will support early planning decisions on clinical development of the compound and will not change the conduct of this study (unless there is a safety concern). After all subjects in a sub-protocol have finished the respective sub-protocol and the data have been locked for that sub-protocol, final analyses for that sub-protocol will be performed. Details of these analyses will be described in the SAP.

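### RA safety tables use one baseline, before the first branebrutinib/placebo dose, so they do not show which laboratory, vital-sign or ECG abnormalities are new after the Week 12 switch to abatacept

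*Combined protocol and SAP*

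**What the plan says.** RA 9.4.2.2 summarises laboratory parameters as absolute values and change from baseline at each visit. It defines baseline once, without limiting it to a study period: "Baseline values are defined as the last nonmissing value prior to the first dose of study treatment". It adds: "Marked abnormalities summarized by visit and shift tables will also be provided". No reference visit is given for the shift tables.

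RA 9.4.2.3 repeats the baseline definition: "Vital signs and ECGs will be summarized as absolute and change from baseline values by visit". RA 6 counts placebo as study treatment, so the baseline is the value before the first branebrutinib or placebo capsule on Day 1.

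The RA safety objective in the RA 1.1 Synopsis is to evaluate "safety and tolerability at Week 24 of switching at Week 12 from branebrutinib or PBO to abatacept". Its endpoint, also in RA Table 4, is "Number and proportion of subjects experiencing SAEs, AEs, and abnormalities in laboratory parameters, vital signs, and ECGs".

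RA 9.4.2 lists the columns for the later period, but only as an option: "After Week 12, data may be presented for the following treatments for the RA sub-protocol". These are branebrutinib then abatacept, placebo then abatacept, and both combined.

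Efficacy is handled differently. RA Table 4 lists "Change from Week 12 to Week 24 in ACR component assessments", and RA 9.3.3 lists Week 12-referenced changes in DAS28, SDAI, CDAI and autoantibody titers as well. hsCRP is one of the ACR components and is also in the safety panel (RA Table 8), so a few laboratory parameters do have a Week 12 reference, as efficacy endpoints.

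**The concern.** A Week 24 change measured from Day 1 is the sum of the change on branebrutinib or placebo (Day 1 to Week 12) and the change after the switch (Week 12 to Week 24). By-visit counts of abnormal values give the total at each visit. They do not say whether the subjects abnormal at Week 24 are the same ones who were abnormal at Week 12.

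For an objective about switching, a reader will ask how many subjects developed an abnormality after starting abatacept, and whether that differs by what they took before. The visible text promises no safety table that answers this. The pSS sub-protocol has the same laboratory paragraph (pSS 9.4.2.2), but it has no switch, so one baseline is enough there.

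**Working it through.** **Plan figure.** The only RA design figure is 82% power for ACR50 (RA 9.1: 60 versus 20 subjects, 45% versus 15%, one-sided 5%). With a pooled rate of (60 × 0.45 + 20 × 0.15)/80 = 0.375, the null SE is √(0.375 × 0.625 × (1/60 + 1/20)) = 0.125. The alternative SE is √(0.45 × 0.55/60 + 0.15 × 0.85/20) = 0.1025. Then z = (0.30 − 1.645 × 0.125)/0.1025 = 0.92, which gives 82%. It reproduces, and this point does not touch it.

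**Inputs below.** The arm sizes 60 and 20 come from RA 9.1. Every abnormality count, SD, correlation and dropout rate is an assumption made for illustration.

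**1. New onset.** Suppose all n subjects are normal on Day 1, a are abnormal at Week 12 and b at Week 24. The number newly abnormal after the switch lies between max(0, b − a) and min(b, n − a).

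| Group | n | a | b | New onset after the switch |
|---|---|---|---|---|
| Branebrutinib then abatacept | 60 | 6 | 6 | 0 to 6 (0% to 10%) |
| Branebrutinib then abatacept | 60 | 6 | 9 | 3 to 9 (5% to 15%) |
| Placebo then abatacept | 20 | 2 | 2 | 0 to 2 (0% to 10%) |

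In the first and third rows the by-visit tables read 10% at both visits in both arms. The difference in new onset between the two sequences could still be anywhere from 0/60 − 2/20 = −10 points to 6/60 − 0/20 = +10 points. If 20% of each arm left before the switch (48 and 16 remain, same counts), the range is 0/48 − 2/16 = −12.5 to 6/48 − 0/16 = +12.5 points. A shift table from Day 1 cannot narrow this, because every subject starts normal. A shift table from Week 12 gives the counts directly.

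**2. Mean and spread of change.** When the same subjects attend, the mean post-switch change is the Week 24 mean change minus the Week 12 mean change, so it is recoverable. Its SD is not. If the Day 1-referenced change has SD s at both visits with correlation r, the SD of the post-switch change is s√(2(1 − r)): 1.18s at r = 0.3, 1.00s at 0.5, 0.63s at 0.8 and 0.45s at 0.9. The planned summaries do not report r.

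**3. Attribution.** Let branebrutinib shift a parameter by d at Week 12, and compare two explanations of what follows. Entries are mean changes at Week 24.

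| Explanation | Branebrutinib arm, from Day 1 | Branebrutinib arm, from Week 12 | Placebo arm, from Day 1 | Placebo arm, from Week 12 |
|---|---|---|---|---|
| Carry-over persists, no abatacept effect | d | 0 | 0 | 0 |
| Full washout, abatacept effect d | d | 0 | d | d |

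The branebrutinib arm looks the same under both explanations, whichever baseline is used. Only the placebo-then-abatacept column separates them.

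**4. Feasibility.** RA Table 2 schedules hematology, chemistry, lipids, urinalysis, lymphocyte subsets, immunoglobulins, vital signs and ECG at Week 12. Dosing comes last in the visit order, so a pre-abatacept value is already collected. HbA1c, as tabulated, has no Week 12 value. Under RA 4.1 the last blinded dose falls on the day before the Week 12 visit, so the Week 12 value is on-drug in the branebrutinib arm.

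**The case against.** The strongest reply is that little is lost.

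- **The endpoint.** It counts subjects with abnormalities; it is not a change score or a new-onset rate. By-visit marked abnormalities address it in part. This stands as far as the literal endpoint goes, but the objective is the switch, and a by-visit total does not separate old abnormalities from new ones.
- **The AE route.** It is broad. RA 8.2.7 sends to the AE page "Any laboratory test result that is clinically significant or meets the definition of an AE or SAE", and also abnormalities that led to treatment interruption, discontinuation or corrective therapy. RA 8.2.8 makes potential DILI, with numerical thresholds, reportable as an SAE. Appendix 3 covers clinically significant ECG and vital-sign results. This stands and confines the point to values not reported as AEs.
- **The SAP.** RA 9.4.4 leaves the details of the final analyses to it, and RA 9.4.2.2 and RA 9.4.2.3 leave the marked-abnormality criteria to it. No SAP is in the text reviewed. A second baseline may already be there.
- **The numbers.** They are illustrative, and the ±10 points pair complete turnover in one arm with none in the other. A Week 12 shift table would also be imprecise: at 3/60 versus 1/20 the Newcombe 95% interval for the difference is about −19 to +10 points. This stands. The table would describe; it would not test.

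A reader might infer that the second baseline would isolate the abatacept effect. It would not, as step 3 shows; the placebo-then-abatacept column does that, and the Day 1 baseline already supports it. A reader might also infer that the shift tables are fixed to Day 1. The text does not state their reference visit; Day 1 is only the baseline that the section defines.

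**Conclusion.** The point holds as a cheap, optional improvement. As written, RA 9.4.2.2 and RA 9.4.2.3 give post-Week 12 change summaries that combine two treatment periods. Neither these nor Day 1-referenced shift tables identify abnormalities that are new after the switch.

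The size is modest: subject-level new onset and the spread of change, for laboratory, vital-sign and ECG values that never become AEs, in descriptive Phase 2a tables. No data are lost, since the Week 12 values are collected.

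The documents do not support reading this as a failure to assess the safety of the switch. AEs, SAEs, absolute values and by-visit abnormalities are all planned, and a mean reversal after Week 12 would be visible.

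The conclusion rests on two assumptions: that the SAP adds no Week 12 safety reference, and, for the new-onset ranges, that the shift tables use the only baseline defined.

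**What to change.** In RA 9.4.2 or the SAP:

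1. Keep the Day 1 baseline for all visits.
2. For data after Week 12, add a second reference, the last nonmissing value before the first abatacept dose. Use it for new marked-abnormality tables, laboratory shift tables and change summaries, limited to parameters measured at Week 12 and later.
3. State the reference visit of every shift table.
4. Change may to will for the branebrutinib-then-abatacept and placebo-then-abatacept columns.
5. Footnote that Week 12 is an on-drug reference in the branebrutinib arm, so changes from it include washout. Add that attribution to abatacept rests on the placebo-then-abatacept column, not on the second baseline alone.

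The cost is a few sentences and one extra set of descriptive tables, with no new visits or samples. The drawback is the washout caveat: without the footnote, a near-zero Week 12-referenced change in the branebrutinib arm could be misread as no abatacept effect. If the SAP already defines a pre-abatacept baseline, only items 3 to 5 need checking.
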